**Table 5: Stopping Rules for Individual Subjects and for the Study**

	State of the Study	Conditions to Meet for Stopping Rules
Criteria for Individual Stopping Rules	Pre-Randomization	
 
• Subject is unable to demonstrate safe use of the study CGM during the run-in phase, as judged by the investigator
 
• Subject fails to demonstrate compliance with using the study CGM during the run-in phase, as defined in the protocol
 

	Pre- and Post-Randomization	
 
• Significant protocol violation or non-compliance
 
• Any severe hypoglycemic event related to the use of the HCL system*
 
• Three severe hypoglycemic events from any cause
 
• DKA unrelated to an infusion site failure and related to the use of the HCL system**
 
• Two episodes of DKA regardless of the cause
 
• Four pump occlusions
 
• Decision by the investigator or the sponsor that termination of study participation is in the subject's best medical interest
 
• Allergic reaction to insulin
 
• Severe allergic reaction to adhesive surface of the infusion set or glucose sensor that prohibits further use of the HCL system
 

Criteria for Total Study Stopping Rules	Pre-Randomization	
 
• Four subjects are unable to demonstrate safe use of the study CGM during the run-in phase, as judged by the investigator
 

	Pre- and Post-Randomization	
 
• Seven severe hypoglycemic events in the total cohort in at least two different subjects
 
• Four DKA episodes in at least two different subjects
 
• Decision by the investigator or the sponsor that termination of study participation is in the subjects' best medical interest
 

Abbreviations: CGM, continuous glucose monitor; DKA, diabetic ketoacidosis; HCL, hybrid closed-loop.

\* A severe hypoglycemic event related to the use of the HCL system refers to the following device deficiencies: CGM transmission failure of low sensor glucose values, an absence of low-glucose alarms when the low-alert function is turned on, or delivery of the maximum basal rate when the sensor glucose is falling that results in a severe hypoglycemic event.

\*\* DKA unrelated to an infusion site failure and related to the use of the HCL system refers to the following device deficiencies: CGM transmission failure of high sensor glucose values, an absence of high-glucose alarms when the high-alert function is turned on, or delivery of the minimum basal rate when the sensor glucose is rising and there is adequate intake of carbohydrates by the research participant that results in a DKA event.

Device-related adverse events will be monitored and addressed promptly. These include:

- 1) a severe hypoglycemic event occurring from CGM transmission failure of low sensor glucose values (SAPT and HCL), an absence of low-glucose alarms when the low-alert function is turned on (SAPT and HCL), or delivery of the maximum basal rate when the sensor glucose is falling (HCL only).
- 2) hypoglycemia <54 mg/dL lasting >20 minutes that did not result in the need for 3rd party assistance but that occurred from CGM transmission failure of low sensor glucose values (SAPT and HCL), an absence of low-glucose alarms when the low-alert function is turned on (SAPT and HCL), or delivery of the maximum basal rate when the sensor glucose is falling (HCL only).
- 3) an episode of DKA unrelated to an infusion site failure and related to CGM transmission failure of high sensor glucose values (SAPT and HCL), an absence of high-glucose alarms when the high-alert function is turned on (SAPT and HCL), or delivery of the minimum basal rate when the sensor glucose is rising (HCL only) and there is adequate intake of carbohydrates by the research participant.
- 4) an episode of DKA related to the absence of an infusion site occlusion alarm (SAPT and HCL) and there is adequate intake of carbohydrates by the research participant.
- 5) hyperglycemia >300 mg/dL lasting >2 hours that did not result in DKA and was not from an infusion site failure but that occurred from CGM transmission failure of high sensor glucose values (SAPT and HCL), an absence of high-glucose alarms when the high-alert function is turned on (SAPT and HCL), or delivery of the minimum basal rate when the sensor glucose is rising (HCL only) and there is adequate intake of carbohydrates by the research participant.
- 6) hyperglycemia >300 mg/dL lasting >2 hours that did not result in DKA but that occurred from an infusion site failure and an absence of an infusion site occlusion alarm (SAPT and HCL) and there is adequate intake of carbohydrates by the research participant.

Should any of these criteria be met, the participant will be given the appropriate replacement device(s) (e.g., insulin pump, transmitter, or sensor). Participants in the HCL arm will be instructed to exit auto mode until replacement device(s) are provided and the malfunction is investigated.

A Data and Safety Monitoring Board (DSMB) will also be established and led by the Safety Officer. The DSMB will be comprised of the Safety Officer (from the University of Colorado), and additional faculty members from outside the BDC (Barbara Davis Center for Diabetes at the University of Colorado) or OSU (Ohio State University) who are selected by the JAEB Center for Health Research. The Juvenile Diabetes Research Foundation (JDRF) is funding this study. JDRF created an Artificial Pancreas Project

Consortium, where artificial pancreas projects include HCL therapy and closed-loop therapy, which is coordinated by the JAEB Center for Health Research. JAEB is an organization that conducts diabetes-related human clinical trials. This partnership allows investigators with artificial pancreas projects funded by JDRF to utilize resources from the JAEB Center for Health Research without added cost to the investigator. For this study, the JAEB Center for Health Research has provided feedback for the Investigational Device Exception application submitted to the Food and Drug Administration, feedback on the statistical analyses, and will work with the study PI and JDRF to form the DSMB. It will be notified immediately of severe adverse events (SAEs). It will review the details of the SAE and the study protocol to determine if the SAE was possibly, definitely, or not related to study procedures. It will advise the study PI of its determination and of corrective action that needs to take place (if at all). The DSMB will be notified of SAEs within 1 business day. They will review the details of the SAE and the study protocol to determine if the SAE was possibly, definitely, or not related to study procedures. It will advise the study PI of its determination and of corrective action that needs to take place (if at all). The study PI will manage and report the SAEs and adverse events (AEs) to the IRB. Additionally, the DSMB will conduct phone or video conference calls every quarter to every 6 months to review all the SAEs and AEs that have taken place. The DSMB will also review the planned interim analyses of data (severe hypoglycemic events) after the first trimester in the first 5 participants of each group.

There are study MDs at each study site who will closely oversee and monitor the study. The study PI will continually review all adverse events during screening, data collection, and insulin delivery with SAPT or HCL therapy. Subjects who fail screening will be informed of the reasons for failure. Adverse events will be reported to the Safety Officer as they occur for each individual occurrence and monthly in aggregate form, as well as documented by standard IRB procedures and reported to them during the annual protocol review. All serious adverse events will be immediately reported to the Safety Officer, COMIRB, OSU's IRB (if applicable), and JDRF using the COMIRB Serious Adverse Report Event (SAE) form. The PI will sign each SAE and include a copy of the signed consent form of the subject with relevant sections highlighted. Serious adverse events are defined as death, life threatening injuries, inpatient hospitalization (other than that related to planned labor and delivery), persistent or significant disability/incapacity, and congenital anomaly/birth defect. All serious adverse events determined by COMIRB to be definitely, probably, or possibly related to the study or intervention will be addressed by COMIRB as appropriate with actions including but not limited to: protocol modification, consent form modification, modification of the timetable for continuing review requirements, new study enrollment suspension, or study suspension or termination. If the study is suspended or terminated, prompt reporting to the JDRF will be provided. Events not requiring suspension or termination shall be reported during the annual progress report.

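### Severe hypoglycemia or DKA caused by named device faults has two unreconciled actions: an individual stopping criterion in Table 5, and device replacement with a temporary exit from auto mode in the text that follows it

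*Combined protocol and SAP*

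**What the plan says.** Both rules stand in the Data and Safety Monitoring Plan in Section IV.C of the combined protocol and SAP.

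**The stopping rule.** Among the individual criteria that apply before and after randomization, Table 5 lists "Any severe hypoglycemic event related to the use of the HCL system" and "DKA unrelated to an infusion site failure and related to the use of the HCL system". Neither needs a second event. Footnote * ties the first to "CGM transmission failure of low sensor glucose values, an absence of low-glucose alarms when the low-alert function is turned on", or to maximum basal delivery while sensor glucose falls. Footnote ** ties the second to "CGM transmission failure of high sensor glucose values, an absence of high-glucose alarms when the high-alert function is turned on", or to minimum basal delivery while sensor glucose rises with adequate carbohydrate intake.

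**The device rule.** After the footnotes comes a numbered list of six device-related adverse events. Item 1 is severe hypoglycemia and item 3 is DKA not due to infusion site failure. A single paragraph then gives the action for any of the six: the participant receives the replacement device or devices she needs. For the closed-loop arm it adds: "Participants in the HCL arm will be instructed to exit auto mode until replacement device(s) are provided and the malfunction is investigated".

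**The concern.** The same event in the same woman meets both rules. Under Table 5 she has met a criterion for being stopped. Under the device rule she gets new equipment and leaves auto mode for a limited time. Supplying a replacement, and giving the exit an end point, make sense only if she goes on.

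These are the device failures with the gravest consequences in the trial. The plan itself calls severe hypoglycemia life-threatening for mother and fetus when it explains the interim analysis. Two sites must apply the rules, and the section on insulin pump adjustments says that procedures should be similar at both. As written, a site can follow one sentence faithfully and depart from the other.

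**Working it through.** The plan states no figure on this point, so the check compares triggers and actions and looks for a rule of precedence.

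**Step 1: are the triggers the same?**

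| Event | Table 5 footnote | Device-related list |
|---|---|---|
| Severe hypoglycemia (footnote *, item 1) | Low readings not transmitted; low alert on but no alarm; maximum basal while glucose falls | The same three faults; the first two marked for both arms, the third for HCL only |
| DKA not from infusion site failure (footnote **, item 3) | High readings not transmitted; high alert on but no alarm; minimum basal while glucose rises; adequate carbohydrate intake | The same faults and carbohydrate condition; the first two faults marked for both arms, the third for HCL only |

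The triggers match. Only the arm labels are added.

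**Step 2: are the actions the same?** Table 5 makes one event an individual stopping criterion. The paragraph after the list replaces the device and, in the HCL arm, suspends auto mode until replacement and investigation. That paragraph exempts no item and does not refer to Table 5. Table 5 does not refer to replacement.

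**Step 3: how far does the conflict reach?**

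- Items 1 and 3 each meet a single-event criterion, so they conflict.
- Item 2 is low glucose without third-party assistance, and items 5 and 6 are prolonged high glucose without DKA. None is severe hypoglycemia or DKA, so none meets those criteria.
- Item 4 is DKA with a missing occlusion alarm. It lies outside footnote ** and would count only toward the criterion of two DKA episodes from any cause.

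The conflict therefore covers 2 of 6 items.

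**Step 4: does another part of the plan settle it?** The opening of the Data and Safety Monitoring Plan has the DSMB review the Table 5 rules, for an individual or for the whole study, and make recommendations on continuation. The DSMB description after the list, repeated under Safety Monitoring in Section D, has the board told of serious events within 1 business day, judge relatedness and advise on corrective action. None of these texts mentions device replacement or says which rule comes first.

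**Step 5: are the terms defined?** Two are not.

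- *Stopping.* Table 5 does not say whether the woman leaves the study or only ends closed-loop use. For the analysis, this decides whether her follow-up ends.
- *HCL system.* Section II names the 670G as the HCL system, and the Study Device text says that this system needs data from open mode. The exclusion criteria speak, before randomization, of changing to it. These uses point to the hardware. Hypothesis SA 1.1, however, contrasts women using the HCL system with women on sensor-augmented pump therapy (SAPT), which points to the randomized therapy. In Table 5 the term could carry either meaning.

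**The case against.** The strongest reply is that the two texts describe stages of one process. The device list is introduced as events to be monitored and dealt with promptly, so its action may be a first response: leave auto mode, replace the faulty part, investigate. Table 5 depends on whether the event was related to the HCL system, which the investigation would inform, and a stopping decision could follow. The action is also one sentence written for six items, four of which raise no stopping question. This reading is coherent and may be what was meant. But the plan states no such order, and the end point given for the exit from auto mode is replacement and investigation, with no mention of a stopping decision.

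A second reply is that sites do not act alone, because the DSMB judges relatedness and advises. That is true and limits how far sites could diverge. It does not tell a site what to do before advice arrives, or which of the two rules the board is to apply.

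A third reply concerns the arms. A reader might infer that Table 5 removes HCL women at a first event while SAPT women with the same sensor fault stay until the rule of three severe hypoglycemic events from any cause applies. The documents do not support that as a finding. All women wear the 670G in SAPT mode before randomization, and the criterion sits in the row that covers both periods. If the term means the hardware, both arms are covered and the arm labels in items 1 and 3 agree with it. This reply stands. What remains is an undefined term.

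**Conclusion.** The point holds in a limited form. For severe hypoglycemia, and for DKA not due to infusion site failure, caused by the named device faults, the protocol states both an individual stopping criterion and a device-replacement path that implies continued participation, and it does not reconcile them. This is more than missing detail, because two stated rules lead to different outcomes for the same life-threatening event.

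Two stronger readings are tempting and should not be drawn:

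- *That the protocol returns the woman to auto mode.* Resumption is implied by the end point of the exit. It is not stated.
- *That the rule biases the comparison of severe hypoglycemia by a calculable amount.* That would need one-sided stopping, which the text does not establish, and a rate of device-caused events, which it does not give. Section III reports 3 severe episodes in 2 women without saying whether they fell among the 28 prospective pregnancies or all 36 analysed (13 + 15 + 8), and attributes none to a device fault. Table 5 also has a study-level criterion of seven severe hypoglycemic events in at least two women, and Section F plans Poisson regression with an offset for follow-up time. Nor are a stopped woman's earlier data lost, since Section F says that the mixed models and Poisson regression use the completed portion.

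The conclusion rests on the wording alone and on no assumed rate.

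**What to change.** Reconcile Table 5 and footnotes * and ** with items 1 and 3 of the device-related list and the action paragraph after it:

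1. Give each of the two events one action, or one ordered sequence that says where a stopping decision and the DSMB's advice fall. Cross-refer the two places.
2. Define individual stopping: leaving the study, or ending closed-loop use with follow-up continuing.
3. Say whether the HCL system in Table 5 means the 670G hardware, and so both arms and the period before randomization, or auto mode only.

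Items 2, 4, 5 and 6 need no change on this account. Which action is right is for the sponsor, the investigators and the DSMB. The cost is a wording amendment and notice to both sites, with no added participants, visits or procedures.

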At the beginning of the 2nd trimester, women will be randomized to HCL therapy or SAPT. Women who were on multiple daily injections at baseline will complete a minimum of 4 weeks of therapy in SAPT mode prior to being randomized. All women in the HCL arm will be trained on the HCL technology. For the first 2 weeks after training, women will be contacted daily for insulin adjustments (if applicable) and trouble-shooting of device wearing. Frequency of insulin adjustments will be guided by glucose levels, level of insulin resistance, and willingness to contact study staff to ask for assistance, where (in general) women with a larger-than-expected number of glucose levels above or below ADA targets, dramatic insulin resistance, and unwilling to proactively contact study staff for assistance will be contacted more frequently for pump follow-up and adjustments as necessary. For the HCL group, insulin adjustments will be changes to carbohydrate-to-insulin doses and/or active insulin time. For the SAPT group, insulin adjustments will be changes to basal rates, carbohydrate-to-insulin doses, correction factors, and/or active insulin time. The first 5 women in each arm of the study will be asked to complete 7-point profiles for 2 weeks after randomization. Women will attend research and clinic visits at the Barbara Davis Center and Ohio State University every 4 weeks for routine diabetes care in pregnancy, downloading of study devices, and outcomes measurements. CGM, glucose meter, and pump downloads will also be reviewed throughout the study to ensure compliance with treatment assignment and the study protocol. Insulin pump adjustments will be made at least once every 4 weeks at face-to-face clinic/research visits and every week in between face-to-face visits, as per routine clinical care. When recommendations for pump adjustments are made during the interim weekly remote monitoring, we will verify that participants correctly entered the new settings. Acceptable forms of verification will include, verbal or written confirmation of new pump settings by the participant, a new upload of settings in CareLink, sending screen shots or pictures of the new settings from the participant’s pump. Women will be contacted every week in between research visits to inquire about open- and closed-loop wear (HCL group) and for pump adjustments as needed (both groups) (See Table 2 and Figure 2). As per routine clinical care, we will recommend that women start low-dose aspirin therapy (81-162 mg orally daily) between 12 and 16 weeks gestations, to reduce the risk of preeclampsia, unless there is a contraindication to aspirin therapy. At the start of the 2nd and 3rd trimesters, women will be given handouts describing conditions of which they should be aware for that trimester (see appendix).

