We will assess safety of HCL therapy by collecting data about episodes of SH requiring the assistance of a 3rd party and time spent <54 mg/dL (SH range), DKA, and skin reactions throughout the study. After the first 5 participants in each group complete 2 weeks of therapy after randomization, we will analyze interim data to compare SMBG measurements for time in the American Diabetes Association's recommended pregnancy target ranges (fasting <95 mg/dL and 2-hour post-prandial <120 mg/dL) and compare groups (see Table 2). Bedtime values will be considered post-prandial if they are within 2 hours of a meal  $\pm$  30 minutes but will be considered fasting (pre-meal) if they are >3.5 hours after a meal. If the average fasting blood glucose levels are 20% higher and the average 2-hour post-prandial values are 20% higher in the HCL arm compared to the SAPT arm, this would be considered worsening of glycemic control in the HCL arm. In the event that these interim analyses demonstrate worsening of glycemic control in the HCL arm, the study would be suspended until further investigation into the safety of the participants is undertaken. After the first 5 participants in each group have completed the 2nd trimester, we will analyze the interim data and compare episodes of SH between groups to ensure no increased risk of SH with HCL therapy (see Table 1). Episodes of SH will be used for the interim analysis as SH events can be life-threatening for pregnant women and their fetuses.

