#### **D. Description, Risks and Justification of Procedures and Data Collection Tools:**

##### Risks:

Wearing insulin infusion sets and sensors can cause adverse skin reactions such as pain at the site of infusion set or sensor insertion. The adhesive pads may cause skin erythema for 1 to 2 days or more. An allergic reaction to 1 or more parts of CSII and CGM devices may occur which can be mild, moderate, or severe (rare). In rare cases, an infection at the infusion set or sensor site may occur. In rare cases, the sensor or needle may break inside the body and would require a minor surgical procedure to remove it.

These risks are likely during the run-in phase, but individuals unable to wear devices will not continue on. We also screen out individuals with a history of serious skin reactions to adhesives. These issues remain possible as the study continues, but will be less likely in those women able to be randomized.

Severe hypoglycemia is defined as a hypoglycemic episode requiring assistance of a 3rd party or hospitalization with or without an SMBG. The risk of severe hypoglycemia is high in pregnancy, especially in the 1st trimester. It will be reported as a severe adverse event (SAE). A hypoglycemic event “requiring assistance” is determined when the subject is unable to treat the event on her own. We have determined our sample size based on the ability to compare rates of severe hypoglycemia between groups. Severe hypoglycemia can lead to coma, seizure, or death, however the likelihood of these extreme adverse events is low. Any untoward event resulting in hospitalization, extension of hospitalization, death, or threat of death will also be considered an SAE. SAEs will be reported to the Drug Safety Monitoring Board (DSMB).

Medtronic CGM systems may experience reduced sensor accuracy (falsely elevated glucose levels) if the user takes acetaminophen-containing products. The level of sensor glucose inaccuracy may vary by participant and may depend on the quantity of acetaminophen administered. Therefore, all participants will be advised to mark acetaminophen use on paper and in the insulin pump as an “Injection” event marker. They will also be advised to rely on fingerstick glucose measurements for 12 hours after acetaminophen use for insulin dosing.

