This study's risks are minimized by use of extensive inclusion and exclusion criteria and close monitoring of research subjects. The key personnel are qualified and experienced in all of the study procedures. The collaborators and consultants provide necessary expertise for ensuring the safety of subjects and the integrity of the study procedures. We will also use a volunteer Safety Officer to oversee the study's safety. The Safety Officer will be an independent investigator (not a member of the research team) with experience in similar clinical research. S/he will review reports of adverse events, recruitment and enrollment statistics (ethnicity and numbers of subjects disqualified, withdrawn, randomized, and who completed the study) every 6 months. This information will be reviewed during meetings with study investigators and recorded by the Safety Officer in meeting minutes. A Data and Safety Monitoring Board (DSMB) will also be established and led by the Safety Officer. The DSMB will be comprised of the Safety Officer (from the University of Colorado), and additional faculty members from outside the BDC or OSU who are selected by the JAEB Center for Health Research. It will be notified immediately of severe adverse events (SAEs). It will review the details of the SAE and the study protocol to determine if the SAE was possibly, definitely, or not related to study procedures. It will advise the study PI of its determination and of corrective action that needs to take place (if at all). The DSMB will be notified of SAEs within 1 business day. They will review the details of the SAE and the study protocol to determine if the SAE was possibly, definitely, or not related to study procedures. It will advise the study PI of its determination and of corrective action that needs to take place (if at all). The study PI will

manage and report the SAEs and AEs to the IRB. Study staff will also identify, evaluate, and report anticipated and unanticipated device-related AEs. Additionally, the DSMB will conduct phone or video conference calls every quarter to review all the SAEs and AEs that have taken place. The DSMB will also review the planned interim analyses of data (especially glucose <63 m/dL) after the first trimester in the first 5 participants of each group.

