#### F. Data Analysis Plan:

##### Statistical Analysis Plan:

Data will be blinded to the study statistician. For the **interim safety analysis**, after the first 5 participants in each group have completed the 1st trimester, we will analyze the interim data to compare episodes of SH between groups to ensure no increased risk of SH with HCL therapy. Episodes of SH will be used for the interim analysis as SH events can be life-threatening for pregnant women and their fetuses. If interim safety analyses demonstrate no increased harm in either group, then the statistician will remain blinded until the end of the study. If the interim safety analyses demonstrate increased harm in one group necessitating evaluation of whether the study should be stopped, then the statistician will be unblinded at that point.

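### The interim between-arm look at severe hypoglycemia is placed, in three of four descriptions, before HCL can have had an effect, and the descriptions disagree on timing and measure

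*Combined protocol and SAP*

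**What the plan says.** Randomization comes late in the study schedule. Section IV.C (Study Design) states: "At the beginning of the 2 nd trimester, women will be randomized to HCL therapy or SAPT". Until then every woman who continues past the run-in uses the pump in SAPT mode.

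The interim SH look is described in four places.

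- Section IV.C, in the safety paragraph before the text on virtual visits: "After the first 5 participants in each group have completed the 2 nd trimester", with SH episodes compared between groups.
- Section F, Statistical Analysis Plan: "after the first 5 participants in each group have completed the 1 st trimester", again comparing SH episodes.
- Section IV.C, Data and Safety Monitoring Plan: the DSMB reviews the "planned interim analyses of data (severe hypoglycemic events) after the first trimester in the first 5 participants of each group".
- Section D, Safety Monitoring: the DSMB reviews the "planned interim analyses of data (especially glucose <63 m/dL) after the first trimester in the first 5 participants of each group".

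Section IV.C and section F give the same purpose: to confirm that HCL does not raise SH risk. Neither gives a number for what counts as increased harm.

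Table 5 contains one numeric study-level SH rule, in the row covering the time both before and after randomization: "Seven severe hypoglycemic events in the total cohort in at least two different subjects". Section D (Risks) adds: "The risk of severe hypoglycemia is high in pregnancy, especially in the 1 st trimester".

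**The concern.** Aim 1 is the safety of HCL against SAPT, and the protocol itself treats SH as potentially life-threatening for mother and fetus. The interim look is the only point during the trial at which the plan asks for SH to be compared between arms. If the section F timing is followed, the 1st-trimester data being compared come from a period when no woman was yet on HCL. The result could then be read as reassurance about HCL when it carries almost no information on it. If the section D wording is followed, the DSMB may receive a different measure from the one the analysis plan promises.

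The seven-event rule does not fill that gap. It adds together both arms and both periods, including the trimester that the protocol singles out for SH risk.

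**Working it through.** **Step 1. Set the four descriptions side by side.**

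| Place | Timing (first 5 per group) | Measure |
|---|---|---|
| IV.C, safety paragraph | after 2nd trimester | SH |
| IV.C, Data and Safety Monitoring Plan | after 1st trimester | SH |
| D, Safety Monitoring | after 1st trimester | mainly glucose <63 mg/dL |
| F, Statistical Analysis Plan | after 1st trimester | SH |

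Assignment happens at the start of the 2nd trimester. Women on injections at baseline need at least 4 weeks of SAPT first, which can only delay it. Events up to the end of the 1st trimester therefore cannot be caused by assigned HCL. Only the safety paragraph in IV.C gives a time at which the first 5 women per group have been through a period of assigned treatment.

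**Step 2. Does the seven-event cap compensate?** The plan gives no derivation for seven, so there is no figure to reproduce. Two checks follow.

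*Without any assumed rate.* Suppose 6 of 12 HCL women and 0 of 12 SAPT women each have one post-randomization event. The total is 6, below 7, although Fisher's two-sided p is 0.014 (0.011 for 6/10 against 0/10). Seven events all before randomization would meet the rule. The example needs six different women: with 2/12 against 0/12 affected, p is 0.48.

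*Illustration with an assumed rate.* Inputs:
- SH rate r per pregnancy: 3 events (in 2 women) over 28 prospective or 36 analysed pregnancies in the preliminary study, so 3/36 = 0.083 to 3/28 = 0.107.
- n = 10 to 12 per arm (20 completers, up to 24 randomized; equal allocation assumed).
- Share s of risk before randomization: 0 to 0.5, assumed.
- Rate ratio RR for HCL after randomization: 1 or 3, assumed.

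Pooled Poisson mean = 2nrs + nr(1−s)(1+RR).

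- RR = 3, n = 10, r = 0.083, s = 0.5: mean 0.833 + 1.667 = 2.5; P(≥7) = 1.4%.
- RR = 3, n = 12, r = 0.107, s = 0: mean 5.14; P(≥7) = 25.9%.
- RR = 1: means 1.67 to 2.57; P(≥7) = 0.2% to 1.6%.
- At r = 0.2 and RR = 3: 39% to 84%.

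The exact 95% limits for 3 events are 0.619 and 8.767, so r could lie between 0.619/36 = 0.017 and 8.767/28 = 0.31. Over that interval P(≥7) at RR = 3 runs from about 0 to 99%.

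**Step 3. What can the look show once moved to the end of the 2nd trimester?** Let f be the share of post-randomization risk that falls in the 2nd trimester, assumed 0.3 to 0.7, with s = 0 or 0.5. The SAPT mean is 5r(1−s)f, and the HCL mean at RR = 3 is three times that.

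- Lowest HCL mean: 5 × 0.083 × 0.5 × 0.3 × 3 = 0.1875; P(no HCL event) = e^(−0.1875) = 83%.
- Highest HCL mean: 5 × 0.107 × 1 × 0.7 × 3 = 1.125; P(no HCL event) = e^(−1.125) = 33%.
- P(more HCL than SAPT events): 16% to 55%. With no true difference (RR = 1): 6% to 23%.
- P(at least 3 HCL events, and more than SAPT): 0.1% to 10%.

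The corrected look is weak but informative. Requiring three HCL events would remove most of what it can show.

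**The case against.** A reader might infer that the pooled rule in Table 5 is itself the fault, or that nobody would see an excess in the HCL arm. The documents do not support that. A cap on all events protects participants, and counting both arms and both periods makes it act sooner. Other safeguards also stand:

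- One SH event due to a listed HCL device deficiency, or three SH events from any cause, stops an individual woman.
- The investigator or sponsor may stop the study.
- Device-event monitoring separates mechanisms specific to HCL from those shared by both arms.
- The DSMB hears of each SAE within 1 business day, judges relatedness and advises on action. SH is reported as an SAE.
- Only the statistician is blinded, and is unblinded if harm needs evaluation.

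Section IV.C and section F also do require an arm comparison of SH, so the plan is not silent on it. SH is not the only by-arm interim look either. A self-monitored glucose look two weeks after randomization has a criterion ("If the average fasting blood glucose levels are 20% higher and the average 2-hour post-prandial values are 20% higher in the HCL arm") that leads to suspension, although it detects high glucose, not SH.

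A reader might also infer that the 1st-trimester look is certain to contain no HCL exposure. That is not established. Groups exist only after randomization and screening runs over 10 months, so women randomized early could have some HCL time by the date the look is run. The supportable statement is little or no exposure.

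None of this resolves the conflict in timing and measure. The individual rules and SAE reviews judge single events or single women, and none compares the arms. The DSMB's report layout is not in the documents, so they do not show whether its routine reports would split events by arm.

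**Conclusion.** The concern holds for the interim SH look. As written in section F and in both DSMB descriptions, it falls too early to do its stated job; one of those descriptions also stresses another measure. This follows from the text and needs no assumed rate.

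The seven-event cap is legitimate but does not substitute for the look, because it separates neither arms nor periods. How often the cap would miss a real HCL excess cannot be pinned down. The 1–26% figure rests on a rate from 3 events in 2 women, independent Poisson events, an assumed 3-fold excess and an assumed pre-randomization share; it ignores withdrawal after three events and this trial's exclusion of women with recent SH. The range of about 0–99% over the rate's confidence interval means that no single value should be relied on.

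Nor do the figures support a fixed minimum number of HCL events at a look with 5 women per arm. This is a point to consider: safety-relevant and easily corrected, but not a threat to the trial's main analysis.

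**What to change.** 1. In section F, in the Data and Safety Monitoring Plan, and in Safety Monitoring under section D, state that the interim SH look takes place once the first 5 women per group have completed the 2nd trimester, as the safety paragraph in IV.C already says.
2. In section D, make SH the measure, as in the other three places.
3. At that look and at routine DSMB reviews, show post-randomization SH events and women affected by assigned arm, with follow-up time. Show pre-randomization events separately.
4. Say that any excess in the HCL arm at the look prompts DSMB discussion, without a minimum of three HCL events.
5. Keep the seven-event cap unchanged.

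The cost is wording in three places and slightly more work on the DSMB report; SH reports and treatment assignment are already part of the study record. Discussion would sometimes be prompted without cause: 6–23% of the time under the pilot-rate assumptions with no true difference. The look would also come later than section F's literal timing. Until then, SAE notification, the individual stops and the two-week glucose look remain in force.
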